IDI participants will be sampled purposively from our pool of existing RCT participants. Through this amendment our consent form will allow participants to endorse interest in an IDI; for those endorsing interest, we will invite participants based on their baseline answers to questions on drinking, sexual activity and contraceptive use, but also other experiences in the pandemic – for example, housing, work, or educational experience, vaccine beliefs and experiences, or personal experience of the disease.

Our project staff will send out a Qualtrics survey asking interested participants if they would like to participate in the IDIs. Participants will be randomly selected and will be given an option to either participate in cross-sectional or longitudinal IDIs. This process will continue until we meet the threshold of 8 participants for each format of IDIs. Once this process is completed, our project staff will set up time for the IDIs. Participants will have an option for conducting interviews over telephone or over zoom depending on their technological bandwidth. The IDIs will be audio recorded. At the end of the interview, participants in the longitudinal interviews will be asked to set up a time/date for the next interview. Cross-sectional IDI participants will be thanked for their participation. Additionally, we will resume the same recruitment process for cross-sectional IDIs every 6 months for next 24 months. Participants will receive \$40 in amazon gift card at the completion of each interview.

M. Supplement Data Analysis

IDI recordings will be deidentified, transcribed, and analyzed using NVivo. Two coders familiar with the study will code the data to maintain reliability and methodological coherence of the qualitative data. We will use a combination of inductive and deductive coding approaches. The primary coder will begin by carefully analyzing the transcripts through the process of inductive or open coding. This process allows the primary coder to code data, categorize the codes, and reorganize the categories thematically. Next, the secondary coder will code the transcripts utilizing the major themes. In addition, the secondary coder will also look for additional emergent themes. To ensure the reliability of the findings of the study, both coders will discuss emergent themes with the study lead. Kappa scores for each theme will be calculated to assess interrater reliability.

N. Supplement Description, Risks and Justification of Procedures and Data Collection Tools: Description_Risks and justification:

As with any electronically based system, our electronic data could be hacked. Thus, potentially compromising confidentiality and privacy. However, we have a strong system in place to guard against such possibilities, including the use of University-sanctioned electronic data collection systems. Further, any data stored on university servers (in locked rooms) will be accessible only by password and usernames, and only by research staff. The justification for using this system is immense. It offers an innovative way to increase research participation by a vastly under-represented population, while also providing services that are culturally tailored to individuals who may not otherwise have access to such services.

O. Supplement Potential Scientific Problem

For the IDIs, we are drawing participants from the existing pool of RCT participants. While the IDIs focus on participants who are at-risk for AEP, the RCT includes participants who are not at-risk for AEP. Therefore, it is possible to not have a sufficient number of participants who are at-risk for AEP in our pool of RCT participants limiting our chance of adequately recruiting enough participants for the IDIs.

P. Supplement Summarize Knowledge to be Gained:

If successful, the supplement will provide us with a greater contextual understanding around patterns of drinking, sexual activity and contraceptive use among urban AIAN young women during the evolving COVID-19 pandemic.

References:

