Fetal Alcohol Spectrum Disorders (FASD) result in neurodevelopmental deficits and lifelong disability; they are a leading cause of preventable birth defects in the U.S.^{1,2} According to the CDC, any sexually active woman of reproductive age who drinks alcohol and does not use effective contraception is at risk for an alcohol exposed pregnancy (AEP) that could cause FASD.² By this definition, American Indian and Alaska Native (AIAN) young women are especially vulnerable. AIAN girls initiate alcohol use earlier than their non-AIAN peers;³⁻⁶ they are also more likely to have used alcohol in their lifetimes, in the last 30 days, and on a daily basis. Concomitantly, compared to all other race groups, high school-aged AIAN girls report the highest levels of ever having had sex (69%), and having had sex in the last 3 months (50%). Across all AIAN youth, 32% reported using alcohol or drugs before last sex, the highest rate across all race groups, and 80% reported not using effective contraception at last sex.89 Unsurprisingly, the birth rate for AIAN women ages 15-19 is 27 per 1000—the third highest rate after non-Hispanic Blacks and Hispanics. 10 One study estimates that 25% of these teen births are substance involved, with the most common substance, alcohol, accounting for more than half of these. 11 While an estimated 72% of AIAN young women live in urban areas, 12 research relevant to AEP is largely based on reservation samples. 13-15 With rare exceptions, 16-20 the research base for urban AIAN youth and young adults remains thin. Urban AIANs tend to live not in concentrated neighborhoods but rather dispersed across the urban landscape; thus, common community-based recruitment and intervention strategies are expensive or rarely applicable for research engagement of urban AlANs.²¹ Consequently, urban AlAN needs are often ignored in research aimed at developing, implementing, and evaluating culturally appropriate services. Recent research indicates that mobile health (mHealth) interventions are promising for delivering effective interventions to hard-to-reach populations.²²⁻²⁴ The goal of this project is thus to expand reach and services to urban AIAN young women through mHealth technology to prevent AEP and FASD.

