- SA2: **Translate AIY-C for mHealth delivery** through an iterative and theoretically driven process, integrating urban AIAN young women's input to enhance cultural and health engagement content and responsiveness; we will pilot and refine the translated mHealth AIY-C intervention.
- SA3: Recruit 700 (final N=525) urban AIAN young women using the refined social media strategies, and conduct an RCT to **rigorously evaluate the effectiveness of the mHealth translation of AIY-C** for preventing AEP and FASD.

SAs 1 and 2 were conducted under a separate COMIRB protocol (#18-0574) as preparatory to research efforts. For this protocol, we focus only on SA 3.

II. Background and Significance:

In the US, an estimated 1 in 8 pregnancies are exposed to alcohol.³⁸ In any given month, 2 million women, about 1 in 30, are at risk of AEP that could result in FASD.³⁹ FASD include FAS, partial FAS, alcohol-related birth defects, and alcohol-related neurodevelopmental disorders.⁴⁰ Children born with FASD suffer cognitive, physical, and social-emotional consequences throughout life; social and financial costs are enormous to individuals and society⁴¹⁻⁴⁶ Rates of drinking among pregnant AIAN women exceed those of other groups,⁴⁷⁻⁴⁹ with rates of 30%¹⁵-43%⁵⁰ in some samples. Prevalence estimates for FASD in AIAN communities are limited and often dated but exceed other groups by at least 2 or more times.^{48,51,52}

Given these data as well as a strong commitment to the health of future generations, tribal communities prioritize youth AEP prevention. AIAN youth are at-risk for initiating alcohol use at younger ages relative to their non-AIAN peers while patterns of use among AIAN youth who drink are more likely to put their own health and that of an unborn child at risk. High school AIAN girls are more likely to have drunk alcohol prior to age 13, currently drink, and drink 5+ drinks at a time compared to those in all other race groups. AEP data for AIANs are limited due to insufficient sample sizes in large national studies; however, the rates cited here confer risk for AEP when coupled with the early and unprotected sexual activity documented for AIAN youth. While over 70% of AIANs live in urban areas, little research exists on patterns of AEP among urban AIAN young women in particular. What does exist indicates that they may be at the same or greater risk for alcohol use and sexual risk compared to their non-AIAN counterparts.

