Studies/Progress Report: Adapted AIY-C intervention content. AIY-C integrates tribal values with guidance about young women's sexual health along with core messages about alcohol use and effective contraception from the original CHOICES curriculum. Given its applicability and relevance for all young women regardless of alcohol use or sexual activity, AIY-C adds messages to support young women who may choose to abstain from sex. Given AIY-C's focus on young women, messages about alcohol convey that no safe level of drinking exists for those under 21. In Table 3 we outline the AIY-C components (CHOICES core components) and their cultural, developmental. and universal adaptations that the CBPR methodology produced. We worked closely with our advisory

Table 3 AIY-C Selected components and adaptations

Table 3. AIY-C Selected components and adaptations		
	AIY-C Components	Cultural/ Developmental/Universal Adaptations
Session 1	Introduction: What is it? How does it	Relevance for young Native women, simplified
	work? How does it help?	language, scope of intervention broadened
	Reflection on 7 Teachings of Anishinaabe:	AIY-C specific cultural teachings emphasizing
	Love, honesty, respect, kindness, humility,	wellness and balance; reflections on
	bravery, wisdom	presence/absence/relevance of teachings
	Reflection on Medicine Wheel: Spiritual	AIY-C cultural heuristic emphasizing spiritual
	(North); Emotional (South), Physical (East),	wholeness and balance; participants asked to
	Mental (West)	reflect on alcohol's impact in key spiritual realms.
	Important Facts for Young Women: Safer	Simplified language, universal language about
	sex, birth control, and pregnancy	sex, condom use, safer sex practices, STD risks
	Daily Journaling: Instructions.	Online for security. added questions: offered
	,	drink/sex, safer sex practices, thoughts/feelings
Session 2	Personal Feedback: Alcohol risk, cost, and	Review of offers to drink, alcohol risk assessment
	calories	based on any drinking
	Personal Feedback: Birth control & safer	Review of offers to have sex, STD risk assessment
	sex, pregnancy, AEP, and STD Risk	
	Personal Goals: Alcohol	Continuing NOT to drink as goal for those who do
		not drink; cultural supports for goal attainment
	Change Ruler: Birth control & Safer sex	Added safer sex practices
	Personal Goals: Birth control & Safer sex	Continue NOT to have sex a goal for not sexually
		active, safer sex goals, cultural supports for goals

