NWC mobile app. Findings from our IDIs informed the content to include in our mobile app. The app contains six sessions; these sessions include content on alcohol use, birth control and safer sex, and facts of AEP and FASD. The app also includes culturally relevant imagery such as the medicine wheel and connections across generation. Motivational interview elements of tone, assessment of personal risk, decisional balance exercises, and goal setting are also included. Participant knowledge of alcohol and birth control methods, including condoms, is assessed through the app. See Appendix A for a selection of images from the App.

IV. Research Methods

We propose using an RCT with a baseline sample n=700 urban AIAN young women aged 16 to 20 to evaluate NWC for its effectiveness in AEP prevention.

Figure 1. NWC Conceptual Model

Outcome Measure(s): Figure 1 depicts the measures used the assess the impact of NWC. These measures include demographics, such as age, education level, and income, measures of social risk; environmental support; and cultural identity. Theoretical mediators include knowledge of effective contraception and alcohol use during pregnancy and self-efficacy related to sexual activity and contraceptive and alcohol use. Our primary outcomes include sexual activity, abstinence, effective contraceptive

use, and alcohol and other substance consumption—AEP protective and risk factors. With the pandemic, we have also added measures on experiences with COVID-19 to capture appropriate context.

B. Description of Population to be Enrolled:

Our population of focus will be AIAN women, ages 16-20, who live in urban areas (50,000 people or more), and who are not pregnant or breastfeeding at the time of enrollment. Currently, we are awaiting approval from the Southcentral Foundation of Alaska, a research review IRB for Alaska Native healthcare in

Anchorage (the only urban area in Alaska with population > 50,000). Until we receive this approval, we will exclude residents from Alaska.

C. Study Design and Research Methods

Screening

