Fidelity. Since intervention content will be administered electronically, we anticipate full fidelity. We expect full adherence, and we will be able to monitor closely progress towards this goal. However, we will track occurrences of technological challenges (e.g., lost devices, or navigational issues), or other unanticipated events with respect to the intervention content delivery.

Post-intervention follow-up retention plans. After the intervention, when surveys are months apart and risk of attrition is high, we have integrated additional retention plans. Every two months, we will offer a small

incentive (e.g., \$10 gift card) to participants who confirm their contact information.

Throughout the project, we will use electronic data to monitor study participation. As data are accrued across the rolling sample, we will use electronic data to monitor sample intake, responses rates, and baseline equivalency.

RCT timing. Recruitment will begin PY3 (see "Timeline," below). We anticipate a rolling recruitment across 2 years. This roll-out will allow sampling strategy adjustment as needed.

Procedures/modes of data collection. Once IRB approvals are obtained, we will begin implementation. We will use the University's Qualtrics survey system, a HIPAA-compliant and secured software for research which can be optimized for smartphones or other devices. As noted above, eligible participants who provide consent will be sent a unique URL to complete a baseline survey. Through the tracking software, we will issue additional URLs for follow-up surveys at the appropriate time. Participants will be compensated \$25 for baseline and the first post-intervention survey, increasing to \$35, \$40, and \$50, respectively, for each of the 3 follow-up surveys. Participants will not be re-consented at each survey point; still, at each survey, participants will be reminded that participation is voluntary, and they can decline participation at any time.

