Intervention and survey progression. After the baseline survey, participants will be asked to download the app using their email and a password, so we can track their registration and ultimately link app use with survey data (e.g., to check number of sessions responded engaged in). We will incentivize the app download with a small e-gift card (\$10). Once registered, the app will randomize participants and they can immediately begin their first intervention sessions (NWC or counterfactual). Once participants have progressed through their respective programs, each will be given an additional small e-gift card (\$10), and, 2 months later, a URL for the first posttest. Similarly, at 6 and 12 months after program completion, each will be sent URLs to complete a survey.

We will regularly monitor electronic reports of progress through the intervention (for NWC), and survey completion progress for follow-up (both arms). Survey data will be routinely checked by the Data Management team for any problems, inconsistencies, or missing data. They will routinely summarize response rates for each survey, and by arm. If response rates are low, or unbalanced by arm, Drs. [name] and [name] will identify possible causes, their solutions, and quickly implement changes to rectify deficiencies.

D. Recruitment

The primary method of recruitment will be through multiple social media platforms. Specific recruitment activities will vary across the platforms, but will typically include posts to promote the program and study. We will also use seed recruitment, and encourage AIAN young women participants to invite their peers and family members to sign up for the program (i.e., chain referral, up to 3).

We will ask the participants enrolled in the study to follow our page on Instagram, share our recruitment post on their Instagram page and tag us in that post. This strategy will amplify our recruitment post among their followers (who may be similarly eligible) and encourage participation in our study (as the recruitment post will have come from a trusted source). This is completely voluntary and the recruitment post does not require participants to disclose any personal health information.

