G. Data Analysis Plan:

All intervention effectiveness analyses will be based on an intention-to-treat approach. For continuous outcomes (frequency/quantity indices of alcohol) and mediational outcomes (alcohol and contraceptive self-efficacy), we will estimate a series of latent growth curve models (LGCM) in Mplus to assess the effect of intervention exposure on the trajectories of those outcomes over the study period. The "normative" trajectory of an outcome is estimated for the comparison group before estimating the same trajectory among those exposed to the intervention. The third step estimates the degree to which the normative growth trajectory is altered by intervention exposure. On the fourth and final step, the interaction between intervention exposure and pre-intervention status on the outcome is tested. This permits an assessment of the differential effectiveness of the intervention as a function of baseline levels of the outcome variable.

For dichotomous outcomes, Latent Markov Models (LMM) will be used to evaluate transitions between behavioral states (e.g., sexually active to abstinent) throughout follow-up. 166,167 Intervention status is modeled as a time-invariant covariate; its effect on the transition probabilities is estimated freely. Effectiveness is indicated if those in the intervention have significantly lower probabilities than the controls of transitioning out of the abstinence state and significantly higher probabilities of transitioning out of the sexually active state. LMM may also reveal that early sexual experience among control group participants predicts sexual activity across the course of the study but that this relationship is interrupted among intervention participants. Other moderators of intervention effectiveness will also be explored (e.g., enculturation).

H. Summarize Knowledge to be Gained:

If successful, the overall study will generate evidence of NWC effectiveness for AEP prevention by demonstrating: 1) increased effective contraceptive use or sexual abstinence among urban AIAN young

women; 2) decreased or eliminated alcohol use in urban AIAN young women who drink; and 3) maintained abstinence (sexual or alcohol) among those who have this as their goal. If successful, the project will also provide vital information about the feasibility of mHealth interventions for reaching urban AIAN young women or other urban AIAN populations who might otherwise not access health information or interventions

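### The aim is prevention of alcohol-exposed pregnancy, but the visible plan never makes the joint at-risk state an outcome, a model state or a success criterion

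*Combined protocol and SAP*

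**What the plan says.** **Aim.** Specific aim 3 is to "rigorously evaluate the effectiveness of the mHealth translation of AIY-C" in preventing AEP and FASD. Section IV opens by saying the RCT is "to evaluate NWC for its effectiveness in AEP prevention".

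**Definition.** The introduction, citing the CDC, states that "any sexually active woman of reproductive age who drinks alcohol and does not use effective contraception is at risk for an alcohol exposed pregnancy". All three conditions must hold in the same woman.

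**Outcomes.** Under Outcome Measure(s): "Our primary outcomes include sexual activity, abstinence, effective contraceptive" use, and alcohol and other substance consumption. These are described as protective and risk factors for AEP. No combined outcome is named.

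**Analysis.** Section G plans latent growth curves for the alcohol frequency and quantity indices, and latent Markov models for dichotomous outcomes. It works out one criterion only: "Effectiveness is indicated if those in the intervention have significantly lower probabilities than the controls of transitioning out of the abstinence state", together with a higher probability of leaving the sexually active state.

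**Interpretation.** Section H says AEP-prevention effectiveness would be shown by three things: more effective contraception or sexual abstinence; less or no drinking among women who drink; and maintained abstinence, sexual or alcohol, in women who have that goal. It gives no test, threshold or rule for combining them.

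**Population.** The program was adapted for its "applicability and relevance for all young women regardless of alcohol use or sexual activity". Section O confirms that the RCT includes women not at risk for AEP.

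**The concern.** The plan states a joint concept, makes it the aim, and then does not measure the aim by it. In a sample made up only of women at AEP risk, any woman who stopped one of the three behaviours would leave the at-risk state, so components and joint risk would be closely tied. In a universal sample they come apart. A contraception gain may fall mainly in women who do not drink, and a fall in drinking mainly in women who are not sexually active or who already use contraception.

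At stake is the headline claim. As section H stands, a significant component result could be reported as evidence of AEP prevention when the proportion at AEP risk has not moved. Conversely, a real fall in joint risk could be spread over several components and never be estimated as such.

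**Working it through.** **1. Search for the joint state.** It appears in the introduction as a definition. It does not appear in Outcome Measure(s), in section G as an outcome or model state, or in section H as a standard of evidence. Section H's first item links contraception with sexual abstinence, but alcohol remains a separate item.

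**2. The plan's own figure.** The plan gives none for AEP risk. The sample sizes (700 recruited, 525 final) imply 1 − 525/700 = 25% loss. The visible text gives no alpha, power, effect size or outcome rate behind them.

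**3. Illustrative inputs.**
- Sexually active, s = 0.50 (introduction: high-school girls, last 3 months).
- No effective contraception, u = 0.80 (introduction: all AIAN youth, at last sex). This is a different group from the one that gives s.
- Drinking, d = 0.30, assumed; 0.20, 0.40 and 0.50 are also tried.
- The three are taken as independent, which is also assumed.

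Starting AEP risk = s × u × d = 0.50 × 0.80 × 0.30 = 0.12.

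**4. A 15-point contraception gain among sexually active women (u from 0.80 to 0.65).**
- Evenly spread: 0.50 × 0.65 × 0.30 = 0.0975.
- All in drinkers: u among drinkers = 0.80 − 0.15/0.30 = 0.30, so 0.50 × 0.30 × 0.30 = 0.045.
- All in non-drinkers: unchanged at 0.12.

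| Assumed drinking | Start | Evenly spread | Range |
|---|---|---|---|
| 20% | 8% | 6.5% | 0.5% to 8% |
| 30% | 12% | 9.75% | 4.5% to 12% |
| 40% | 16% | 13% | 8.5% to 16% |
| 50% | 20% | 16.25% | 12.5% to 20% |

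**5. Sexual activity falls from 50% to 40%, with d = 0.30.**
- Evenly spread: 0.40 × 0.80 × 0.30 = 0.096.
- All ten points from at-risk women: 0.12 − 0.10 = 0.02.
- None from at-risk women: 0.12.

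The same component result is therefore compatible with a large fall in AEP risk or with no fall.

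**6. Precision if the joint outcome is tested.** Take 525/2, about 262 per arm (1:1 assumed), two-sided 0.05, and a two-proportion test with pooled variance under the null.
- 16% vs 8%, one survey: null SE = √(2 × 0.12 × 0.88/262) = 0.0284; alternative SE = √((0.16 × 0.84 + 0.08 × 0.92)/262) = 0.0282; z = (0.08 − 1.96 × 0.0284)/0.0282 = 0.86; power about 81%.
- 12% vs 6%, one survey: about 67%.
- 12% vs 9.75%, one survey: about 13%. The 95% confidence half-width is 1.96 × √((0.12 × 0.88 + 0.0975 × 0.9025)/262) = 0.053.

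Averaging three complete surveys multiplies the variance by (1 + 2ρ)/3. For an assumed within-woman correlation ρ from 0.7 down to 0.3, power is 89% to 97% for 16% vs 8%, but only 15% to 21% for 12% vs 9.75%.

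**The case against.** The strongest reply is that the plan is broader than its one worked criterion. Section G applies Markov models to dichotomous outcomes generally and offers the sexual-activity transition only as an example. Alcohol has its own growth models, which estimate how exposure alters the trajectory. Section H names contraception and alcohol as well as abstinence. A reader might infer that a woman who stays sexually active but starts contraception or stops drinking counts nowhere, or that the trial judges success on sexual activity alone. The documents do not support either reading: such a woman would contribute to planned component analyses. What stands is that none of those analyses estimates joint risk, and that section H supplies no rule that would.

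Second, the wide ranges come from extreme allocations. The 4.5% end needs non-use among drinkers to fall from 80% to 30% with no change in non-drinkers. When the gain is evenly spread, joint risk moves in the same direction as the component. This is fair: the bounds show what component results leave open, not that distortion is likely here.

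Third, universal prevention is intended, and benefit in women not at AEP risk is a legitimate result. That is accepted. Enrolling them is not a flaw; it is why the two quantities must be kept apart.

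Fourth, Figure 1 is said to depict the measures and is not shown, nor are the survey items. A composite could appear there, although the text introducing the figure names none.

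**Conclusion.** The point holds for the visible text. AEP prevention is the aim and AEP risk is defined as a joint state, but no outcome, model state or success criterion uses it, and section H would treat separate component results as evidence of AEP prevention. This is more than missing detail, because in a mixed-risk sample that inference does not follow. Under the assumed 12% starting risk, a 15-point contraception gain leaves 4.5% to 12% at risk, and a ten-point fall in sexual activity leaves 2% to 12%. Both rest on an assumed drinking rate, background rates from two different youth groups, and independence.

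No figure in the plan is shown to be wrong, and nothing here shows that the component analyses would mislead in this trial. Confidence is moderate because Figure 1 and the survey items cannot be seen. The change is worth making because it needs little beyond behaviours already listed as outcomes.

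**What to change.** Section I describes the RCT as ongoing, so this should be a dated amendment made without sight of outcomes by arm.

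1. Derive a binary AEP-risk outcome from the introduction's definition, using the sexual activity, contraception and alcohol measures already collected, with one stated recall window. This assumes the survey items allow a common window.
2. Pre-state one intention-to-treat between-arm comparison of it, adjusted for baseline AEP risk, and report the estimate with its confidence interval. A repeated-measures logistic model averaged over the 2, 6 and 12 month surveys is one option. The surveys must be named: Intervention and survey progression gives a posttest 2 months after the program and surveys "at 6 and 12 months after program completion", whereas the payment text covers a first post-intervention survey and then payments "respectively, for each of the 3 follow-up surveys".
3. Amend section H so that component results, which keep their planned models, are reported as behavioural effects and are not presented alone as evidence that AEP risk fell.

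The choice of model, any Holm adjustment across components, and whether this outcome becomes the sole primary are left to the sponsor.

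**Cost.** A little more analysis, and no new visits or measures if the recall-window assumption holds. The real downside is limited precision: a halving from 16% is detectable, but an evenly spread change from 12% to 9.75% is not. A null result should therefore be reported as imprecise, with its interval, and not as absence of effect.

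### Four or five primary outcomes are analysed separately, with no stated alpha, no multiplicity control and no rule for how many must succeed

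*Combined protocol and SAP*

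**What the plan says.** The Outcome Measure(s) paragraph under IV. Research Methods gives the list: "Our primary outcomes include sexual activity, abstinence, effective contraceptive" "use, and alcohol and other substance consumption—AEP protective and risk factors". No outcome is singled out, and the verb leaves the list open.

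Section G (Data Analysis Plan) splits the work by outcome type:

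- Continuous outcomes: "For continuous outcomes (frequency/quantity indices of alcohol) and mediational outcomes (alcohol and contraceptive self-efficacy), we will estimate a series of latent growth curve models". Alcohol therefore enters as more than one index.
- Dichotomous outcomes: "Latent Markov Models (LMM) will be used to evaluate transitions between behavioral states (e.g., sexually active to abstinent) throughout follow-up". Sexually active and abstinent are two states of one variable here.

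The only explicit criterion for success concerns sexual activity and has two conditions. The first is "Effectiveness is indicated if those in the intervention have significantly lower probabilities than the controls of transitioning out of the abstinence state". The second, joined to it, is "and significantly higher probabilities of transitioning out of the sexually active state".

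Section H (Summarize Knowledge to be Gained) says that, if successful, "the overall study will generate evidence of NWC effectiveness for AEP prevention by demonstrating: 1) increased effective contraceptive use or sexual abstinence". It then adds two further results, reduced drinking and maintained abstinence.

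Neither section states a significance level, sidedness, a multiplicity procedure, a hierarchy, a composite, or how many outcomes must succeed.

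**The concern.** With several co-equal primary outcomes, separate models and no rule across them, the error rate of an overall claim of effectiveness is undefined. After the data are in, nothing in the plan would let a reader distinguish one success among several from a result that had been specified as decisive.

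Two features of the list make this worse. First, sexual activity and sexual abstinence appear as separate labels for one behaviour. Second, other substance use is primary although section G gives it no analysis. It also lies outside the definition of AEP risk in the protocol's opening paragraph, which rests on being sexually active, drinking alcohol and not using effective contraception.

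**Working it through.** The documents give no alpha, power or familywise error rate, so there is no planned figure to reproduce. The size is worked out under stated assumptions.

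**Inputs**

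- Number of tests, k. Three: sexual activity/abstinence, contraception and one alcohol index. Four: add other substance use. Five: also split alcohol into frequency and quantity.
- Alpha: 5% two-sided per test (assumption).
- Decision rule: any one significant result counts (assumption).
- Correlation between test statistics: 0 or 0.5 (assumption).

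**Formulas under independence**

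- Any false significant result: 1 − 0.95^k.
- A false result in the favourable direction: 1 − 0.975^k.

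The figures at correlation 0.5 come from 1,000,000 simulated draws of equally correlated normal statistics.

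| k | Any direction, independent | Any direction, r = 0.5 | Favourable, independent | Favourable, r = 0.5 |
|---|---|---|---|---|
| 1 | 5.0% | – | 2.5% | – |
| 3 | 14.3% | 12.5% | 7.3% | 6.3% |
| 4 | 18.5% | 15.6% | 9.6% | 7.8% |
| 5 | 22.6% | 18.3% | 11.9% | 9.1% |

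**Effect of the two-condition rule.** The table treats sexual activity as one ordinary test, but section G requires both transition probabilities to differ significantly. If neither effect exists and the two tests are independent, the favourable false-positive rate for that outcome is 0.025² = 0.000625. The favourable-direction rates under independence become:

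- k = 3: 1 − 0.999375 × 0.975² = 5.0%
- k = 4: 1 − 0.999375 × 0.975³ = 7.4%
- k = 5: 1 − 0.999375 × 0.975⁴ = 9.7%

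For a given k, the table is therefore an upper figure. The rates remain two to four times the 2.5% of a single test.

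**After the fix.** With three outcomes, the first Holm threshold is 0.05/3 = 1.67%. The chance of any false rejection when all three nulls are true is 1 − (1 − 0.05/3)³ = 4.9% if independent, and 4.4% at correlation 0.5. A test with 80% power at 5% has a standardised effect of 1.960 + 0.842 = 2.802. At 1.67% the critical value is 2.394, so power is Φ(2.802 − 2.394) = Φ(0.408) ≈ 66%.

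**The case against.** The strongest reply is that section H joins its three results by conjunction. If all three were required, the error would be below that of a single test, and no adjustment would be needed. But section H summarises what would be learned if the trial succeeds; it is not written as a decision rule. It omits other substance use, a listed primary outcome, and its first and third items each offer alternatives. It does not settle what counts as success.

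A second reply is that the two-condition rule already guards the sexual-activity outcome. That is correct, and it lowers the figures as shown. It covers that outcome only; no criterion is given for contraception or alcohol.

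A reader might go further and infer that the plan carries an 18–23% chance of a false finding of effectiveness where 5% was intended. The documents do not support this. They state no alpha. They do not say that one success is enough. The 18–23% range also counts false results in both directions. For five tests, the favourable-direction figure is 9.1–11.9% over correlations 0.5 to 0, and its comparator is 2.5%.

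A reader might also take the first item of section H as two separate chances to succeed. It can equally be read as one protected state, reached by contraception or by abstinence, so no error figure should be built on it.

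**Conclusion.** The gap is real. Four or five primary outcomes are listed and analysed separately, with nothing to bound the error over the set and no rule for overall success. One listed outcome has no named analysis.

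The size is conditional on two-sided 5% tests and on any one success counting, neither of which is stated. On those terms, the chance of at least one false significant result is 14.3–22.6% for three to five independent tests and 12.5–18.3% at correlation 0.5. In the favourable direction it is 7.3–11.9% and 6.3–9.1% respectively, against 2.5% for a single test.

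These are upper figures for a given number of tests. The number itself is not fixed: section G also plans a test of interaction with baseline status and exploratory moderators, and says nothing about how these relate to the primary claim. The matter should be settled before analysis.

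**What to change.** Revise the outcome paragraph and section G as follows.

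1. Count sexual activity/abstinence once, under section G's two-condition rule. For Holm, use the larger of the two transition p-values, with both effects in the favourable direction.
2. Name one alcohol index as primary. Move the other alcohol indices and other substance use to secondary.
3. State the single test that decides each of the three remaining primary outcomes: sexual activity/abstinence, effective contraception and alcohol.
4. Apply Holm at an overall two-sided 5%: the smallest p-value against 1.67%, the next against 2.5%, the last against 5%, stopping at the first failure. State that effectiveness is claimed only for outcomes rejected under Holm.
5. Report maintained abstinence among those with that goal, baseline interactions and moderators as non-confirmatory. Define any such subgroup by baseline status: goal-setting is part of the NWC app, so a group formed by stated goals could arise after randomisation.

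Testing section H's items in their listed order would not be a safe substitute. Nothing marks that order as a priority. If an item with alternatives passed on one rejection and opened the next at full 5%, the error could reach 1 − 0.95² = 9.75%.

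The cost is wording only; no procedure or sample size changes. The downsides are the fall in power from 80% to about 66% at the first Holm step, and the loss of confirmatory status for other substance use and the remaining alcohol indices.
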